8.1.2 Analysis of the primary outcome variable

The number and proportion (%) of subjects who meet the primary endpoint of safe and effective self-injection at Visit 2 will be summarized overall and by dosing group and indication. Subjects who completed dose delivery, and subjects who has no AEs related to use of the e-Device will also be presented. The number of subjects who administered the self-injection at Visit 2 will be used as the denominator to calculate the proportion (%). The corresponding 90% CI based on Exact Binomial method will also be presented.

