12.1 Definition of analysis sets

The Safety Set (SS) will consist of all subjects of the study who have received at least 1 dose of CZP during the study (e-Device).

Safety variables will be analyzed using the Safety Set (SS).

The Full Analysis Set (FAS) will consist of all subjects in the SS who received at least 1 dose of CZP using the e-Device in the study. All outcome variables will be analyzed using the FAS.

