12.2 General statistical considerations

This is an estimation study design with no formal statistical hypothesis testing. The study will estimate the true population proportion and/or mean. Each endpoint will be summarized by dosing regimen (Q2W or Q4W) and by indication.

Summary statistics for continuous variables will include:

- Number of available observations
- Mean, standard deviation, minimum, median, and maximum

For categorical variables, the number and proportion of subjects, along with the 90% confidence interval (CI) based on the Exact Binomial method, will be presented.

The Baseline value is defined as the last nonmissing measurement prior to self-injection at Visit 1. Results from the Cochin Impaired Hand Function questionnaire at Visit 1 will be summarized.

No imputation of missing data will be performed.

All data recorded in the eCRF and questionnaires will be listed.

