12.3.1 Analysis of the primary outcome variable

The primary outcome variable is the proportion (%) of all subjects able to self-administer safe and effective injections using the e-Device at Visit 2. Safe and effective self-injection will be evaluated by the HCP and is defined as:

- Complete Dose Delivery: Subject self-injected the complete dose of CZP as confirmed by a visual inspection of the CZP-cassette(s) which shows the container PFS to be empty and
- No AEs related to use of the e-Device (ADEs) that would preclude continued use of the e-Device for self-injection

For subjects on the Q4W dosing regimen who will self-inject twice ($2 \times 200\text{mg CZP}$) at each visit, each injection will be evaluated for safety and effectiveness using the above criteria. The primary endpoint of safe and effective self-injection for subjects on the Q4W dosing regimen will be met only if both self-injections are determined to be safe and effective.

The number and proportion of subjects with safe and effective self-injections will be tabulated for the FAS overall, by dosing group, and by indication. A subgroup analysis will be performed for subjects in the FAS with impaired hand function. The 90% CIs for the proportion based on the Exact Binomial method will be reported as well.

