12.6 Handling of dropouts or missing data

There will be no special procedures for handling missing data. All imputation of missing or partial dates for safety assessments will be detailed in the Statistical Analysis Plan.

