3.5.2 Full Analysis Set

The Full Analysis Set (FAS) will consist of all subjects in the SS who received at least 1 dose of CZP using the e-Device in the study.

Since SS and FAS have the same definition in this study, the two sets will contain the same population. SS will be used for analyzing both safety variables and outcome variables in all presentations.

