8 OUTCOME ANALYSES

Outcome analysis will be performed on the SS overall and by dosing group and indication. All outcome variables will be listed.

All statistical analysis will be descriptive in nature. There is no formal statistical hypothesis testing or inferential analyses are planned. No p-values will be presented.

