8.1.1 Derivations of primary outcome variable

The primary endpoint of safe and effective self-injection will be met if both criteria are confirmed by the HCP and are recorded on the Study Medication Administration CRF form: (1) subject self-inject the complete dose of CZP as confirmed by visual inspection of the CZP-cassette(s) which shows the PFS container to be empty; (2) there are no AEs related to use of the e-Device (ADEs) that would preclude continued use of the e-Device for self-injection.

No imputation of missing data will be performed.

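### The primary Visit 2 proportion omits subjects who stop after Visit 1, so device-related stops can flatter it; a proportion over the whole FAS should be pre-specified beside it

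*SAP*

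**What the plan says.** SAP 8.1.2 fixes the divisor of the primary proportion: "The number of subjects who administered the self-injection at Visit 2 will be used as the denominator". The result comes with a 90% exact binomial CI, overall and by dosing group and indication. SAP 4.8 and 8.1 add the subgroup with impaired hand function.

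The named analysis set is wider than that divisor. Protocol 12.1 states "All outcome variables will be analyzed using the FAS" and admits to the FAS any subject with at least one e-Device dose in the study. Protocol 12.3.1 says that the successes "will be tabulated for the FAS overall, by dosing group, and by indication". SAP 3.5.2 observes that FAS and SS are the same subjects and concludes: "SS will be used for analyzing both safety variables and outcome variables in all presentations". A subject who injected at Visit 1 and never returned belongs to this set.

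Neither document says how to score that subject for Visit 2. Protocol 12.2 says "No imputation of missing data will be performed", Protocol 12.6 says "There will be no special procedures for handling missing data", and SAP 8.1.1 repeats the bar on imputation.

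The endpoint has two parts. The first is complete dose delivery. The second, in SAP 8.1.1, is that "there are no AEs related to use of the e-Device (ADEs) that would preclude continued use of the e-Device for self-injection".

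**The concern.** A device-related stop between the visits is not ordinary missing data. The second part of the endpoint exists to catch an ADE serious enough to end use of the device, and that same event prevents a Visit 2 injection. Under SAP 8.1.2 the subject is then in neither numerator nor denominator.

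Other device-related losses work the same way. A malfunction without an adverse event is a device deficiency under Protocol 10.2.1.3.3, and does not fail the second criterion. A subject may also fail to return after an incomplete Visit 1 dose. Either could remove a likely failure from the primary result.

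The primary objective is the ability to self-inject safely and effectively at Visit 2. The study has no hypothesis test and no success threshold (Protocol 12.2 and 12.3), so the estimate and its CI are the result. What is at stake is whether they lean towards the device.

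**Working it through.** **Could the situation arise?** The visits are 2 or 4 weeks apart (Protocol 5.1). Withdrawal criterion 8 in Protocol 6.3 covers a severe or serious injection site reaction, or an SAE, that stops further participation. It does not require device-relatedness, so it is a possible route to a precluding ADE and not the same event.

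**Where would the subject be counted?**
- *Primary Visit 2 proportion (SAP 8.1.2):* not counted.
- *Visit 1 proportion (SAP 8.2.1):* counted, since its divisor is all Visit 1 self-injectors. It is a failure if the precluding ADE, or the incomplete dose, was recorded on the Visit 1 administration form. A precluding ADE that emerges after that form is completed can be missed by both proportions.
- *ADE tables (SAP 10.2.2), TEAEs leading to discontinuation (SAP 10.2.1), disposition (SAP 5.1):* counted as applicable. None of these changes the primary proportion.

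**Inputs.** At least 60 subjects using the e-Device at Visit 1, at least 15 per dosing group and at least 10 with impaired hand function (Protocol 12.8). Two-sided 90% exact binomial CI (Protocol 12.3.1). The documents give no number of stops and no planned precision, so there is no stated figure to reproduce. The number of stops, d, is my assumption.

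**Formulas.** Let n be subjects dosed at Visit 1, m = n − d Visit 2 injectors, and s successes among them.
- SAP 8.1.2: s/m.
- Whole FAS/SS with no Visit 2 injection as failure: s/n.
- Difference: s/m − s/n = s·d/(m·n), which is never negative.
- Exact limits: the lower limit solves P(X ≥ x) = 0.05 and the upper solves P(X ≤ x) = 0.05. When x equals the divisor N, the lower limit is 0.05^(1/N); for example 0.05^(1/59) = 0.950 and 0.05^(1/9) = 0.717.

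**Results (90% CI).**

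| Assumed case | SAP 8.1.2 | Whole FAS/SS, stops as failures |
|---|---|---|
| n = 60, d = 0, no Visit 2 failure | 60/60 = 100% (95.1–100) | 60/60 = 100% (95.1–100) |
| n = 60, d = 1, no Visit 2 failure | 59/59 = 100% (95.0–100) | 59/60 = 98.3% (92.3–99.9) |
| n = 60, d = 2, no Visit 2 failure | 58/58 = 100% (95.0–100) | 58/60 = 96.7% (89.9–99.4) |
| n = 60, d = 1, two Visit 2 failures | 57/59 = 96.6% (89.7–99.4) | 57/60 = 95.0% (87.6–98.6) |
| Dosing group n = 15, d = 1, no Visit 2 failure | 14/14 = 100% (80.7–100) | 14/15 = 93.3% (72.1–99.7) |
| Impaired hand n = 10, d = 1, no Visit 2 failure | 9/9 = 100% (71.7–100) | 9/10 = 90.0% (60.6–99.5) |

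Check of the formula on the fourth row: 57 × 1/(59 × 60) = 0.016, matching 96.6% − 95.0%.

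**Mixed losses.** Suppose 60 are dosed and 3 have no Visit 2 injection: one precluding ADE, one malfunction without an adverse event, one unrelated. If all Visit 2 injections succeed, SAP 8.1.2 gives 57/57 = 100% (94.9–100). Adding only the ADE stop as a failure gives 57/58 = 98.3% (92.1–99.9). The whole FAS/SS gives 57/60 = 95.0% (87.6–98.6), which is lower partly because it also charges the unrelated loss to the device.

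**The case against.** The strongest reply is that the SAP made an allowed choice and stated it openly. The protocol gives no divisor, rules out imputation and sets no missing-data procedure. The endpoint is tied to a visit and to the administration form, so an ADE from the Visit 1 injection properly fails the Visit 1 proportion, which has its own 90% CI. With no test, no threshold and no power calculation, one stop in 60 moves the estimate by 1.7 points. The larger shifts are in groups of 10 or 15, whose intervals are wide anyway.

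Most of this stands. It does not remove the direction of the possible bias, or the gap for an ADE that emerges after the Visit 1 form is completed.

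Two stronger readings are tempting, and the documents do not support them:
- *The SAP departs from the protocol.* A reader might infer this because the protocol speaks of all subjects and tabulates for the FAS, while SAP 3.9 declares no changes. But naming an analysis set does not say how a member without a Visit 2 result is scored, and Protocol 12.2 and 12.6 leave room for observed cases.
- *The primary divisor must be redefined so that precluding-ADE stops are failures.* Those stops cannot be identified exactly from the planned listings. SAP 10.2.1 lists relationship to device and whether the event led to discontinuation; neither field records the healthcare provider's judgement that continued use was precluded. Such a divisor would also miss other device-related stops, and could count one event as a failure at both visits.

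**Conclusion.** The point holds as a gap in the primary presentation. SAP 8.1.2 lets device-related stops after Visit 1 leave the primary proportion, which can bias it and its CI in favour of the device. It is not a breach of the protocol, and the stops are not hidden from the report as a whole.

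The size depends entirely on the assumed number of stops. With none there is no effect. With one in 60 and no other failure, the estimate differs by 1.7 points and the lower limit is 95.0% instead of 92.3%. In the minimum impaired-hand subgroup one stop makes a 10-point difference, with a lower limit of 71.7% instead of 60.6%.

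A reader might also infer that only ADE stops matter. That is too narrow, because a malfunction without an adverse event or an incomplete Visit 1 dose can lead to a stop with the same effect. Losses unrelated to the device need not bias the planned proportion.

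**What to change.** In SAP 8.1.2:
1. Keep the proportion among Visit 2 self-injectors as planned.
2. Pre-specify beside it a proportion over all FAS/SS subjects in which no Visit 2 self-injection counts as failure, with the same 90% exact CI and the same breakdowns: overall, dosing group, indication and impaired hand function.
3. List every subject without a Visit 2 injection by reason: ADE, device deficiency or other.
4. Optionally add a supportive proportion in which only stops for device-related adverse events leading to discontinuation are failures, with a note that the SAP 10.2.1 fields are a proxy for the judgement that continued use was precluded.

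The cost is SAP wording, one or two extra proportions and a listing; no new assessments are needed. The whole-FAS figure may be less favourable and is conservative, because it also counts unrelated losses as failures. The listing by reason lets a reader judge how much of any difference is due to the device.

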4 STUDY VARIABLES

4.1 Study outcome variables

4.1.1 Primary outcome variable

The primary outcome variable is the proportion (%) of subjects able to self-administer safe and effective injections using the e-Device at Visit 2. Safe and effective self-injection will be evaluated by the HCP and is defined as:

- Complete Dose Delivery: Subject self-injected the complete dose of CZP as confirmed by a visual inspection of the CZP-cassette(s) which shows the PFS container to be empty and

- No AEs related to use of the e-Device (ADEs) that would preclude continued use of the e-Device for self-injection

During self-injection, if the skin sensor at the injection port loses contact with the skin, the e-Device will withdraw the needle and stop administration of CZP. If less than five minutes have elapsed since loss of contact with skin, the subject can reposition the e-Device on a new clean injection site and resume and complete the self-injection. If the subject is unable to complete the self-injection and deliver the entire dose of medication (ie, the device indicates incomplete administration and the CZP-cassette is not seen to be empty), the HCP evaluating the self-injection will document the incomplete self-injection, note the reason why the complete dose was not administered, and using his/her best medical judgment, advise the subject regarding any further dosing.

For subjects on the Q4W dosing regimen who will self-inject twice (2×200mg CZP) at each visit, each injection will be evaluated for safety and effectiveness using the above criteria. The primary endpoint of safe and effective self-injection for subjects on the Q4W dosing regimen will be met only if both self-injections are determined to be safe and effective.

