2.4 Determination of sample size

This study will not be powered with respect to any endpoint and sample size is based on practical considerations. The number of subjects and their diagnosed conditions are summarized below.

Approximately 80 subjects who are currently being treated with commercial CZP and are on a stable dosing regimen for at least 3 months will be screened in order to have at least 60 subjects use the e-Device at Visit 1. The 60 subjects using the e-Device at Visit 1 will be composed of a minimum of 15 subjects in each of the dosing groups (Q2W vs Q4W) with a minimum of 15 subjects with CD and a minimum of 10 subjects with impaired hand function. Impaired hand function will be measured using the Cochin scale (Poiraudieu et al, 2000; Duruöz et al, 1996) and impaired hand function will be defined as patients who have a Cochin score ≥13.5 at baseline.

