3.5 Analysis sets

3.5.1 Safety Set

The Safety Set (SS) will consist of all subjects of the study who have received at least 1 dose of CZP during the study (e-Device).

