8.2 Statistical analysis of the secondary outcome variables

The secondary outcome variables will be summarized using descriptive statistics. All summary statistics will be presented overall and by dosing group and indication. A subgroup analysis will be performed for subjects with impaired hand function.

8.2.1 Proportion (%) of subject able to self-administer safe and effective injections at Visit 1

Safe and effective self-injection will be evaluated by the HCP at Visit 1 and is defined as:

- Complete Dose Delivery: Subject self-injected the complete dose of CZP as confirmed by a visual inspection of the CZP-cassette(s) which shows the PFS container to be empty and
- No AEs related to use of the e-Device (ADEs) that would preclude continued use of the e-Device for self-injection

For subjects with CD on the Q4W dosing regimen who will self-inject twice (2x200mg CZP) at each visit, each injection will be evaluated for safety and effectiveness using the above criteria. The endpoint of safe and effective self-injection for subjects on the Q4W dosing regimen will be met only if both self-injections are determined to be safe and effective at Visit 1.

The derivation of this secondary endpoint will follow the same algorithm as the derivation of the primary endpoint. No imputation of missing data will be performed.

The number and proportion (%) of subjects who meet the endpoint of safe and effective self-injection at Visit 1, as well as subjects who completed dose delivery, and subjects who has no AEs related to use of the e-Device will be summarized overall and by dosing group and indication. The number of subjects who administered the self-injection at Visit 1 will be used as the denominator to calculate the proportion (%). The corresponding 90% CI based on Exact Binomial method will also be presented.

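### A trained subject to whom the e-Device never delivers drug is outside both success proportions, and a device-related missed Visit 2 attempt drops out of the primary

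*SAP*

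**What the plan says.** **Analysis sets.** SAP 3.5.1 defines the Safety Set (SS) as "all subjects of the study who have received at least 1 dose of CZP during the study (e-Device". Protocol 12.1 puts the same condition on the other set: "The Full Analysis Set (FAS) will consist of all subjects in the SS who received at least 1 dose of CZP using the e-Device". SAP 3.5.2 notes that the two coincide and concludes that "SS will be used for analyzing both safety variables and outcome variables in all presentations". SAP 8 repeats this: "Outcome analysis will be performed on the SS overall and by dosing group and indication".

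**Denominators.** For the primary, SAP 8.1.2 states: "The number of subjects who administered the self-injection at Visit 2 will be used as the denominator to calculate the proportion". For the Visit 1 secondary, SAP 8.2.1 states: "The number of subjects who administered the self-injection at Visit 1 will be used as the denominator to calculate the proportion". SAP 8.1.1 rules out imputation.

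**Protocol counterpart.** Protocol 12.3.1 describes the primary as the proportion of all subjects and tabulates it for the FAS, with no condition on injecting at Visit 2. SAP 3.9, on changes to protocol-defined analyses, reads as not applicable.

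**Recruitment target.** Approximately 80 subjects "will be screened in order to have at least 60 subjects use the e-Device at Visit 1" (SAP 2.4), including at least 10 with impaired hand function. The target counts use of the device, whereas the analysis sets count receipt of a dose.

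**The concern.** The study asks whether trained subjects can deliver their dose safely with the e-Device, and complete delivery is the first of the two success criteria. A set that admits only subjects who received a dose is therefore conditioned on part of the outcome. The most complete failure, no drug at any attempt, removes the subject from the analysis when it should count against the device. Such a subject can fill one of the 60 places and still not be analysed.

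The Visit 2 denominator has a related effect. An adverse device effect (ADE) that precludes continued use is the second failure criterion. Yet if it occurs at Visit 1 and the subject does not inject at Visit 2, the subject is absent from the primary result.

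At stake is an optimistic point estimate and interval. The effect per subject is largest in the hand-impaired subgroup, which has a planned analysis and only 10 guaranteed subjects.

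**Working it through.** **Step 1: who enters each proportion under the text as written.**

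| Subject | In SS/FAS? | Visit 1 proportion | Visit 2 proportion (primary) |
|---|---|---|---|
| No drug delivered at any attempt | No | Absent | Absent |
| Dosed at Visit 1, no Visit 2 attempt for a device-related reason | Yes | Present; a failure if the Visit 1 injection failed | Absent |
| Dosed at one visit, attempt with no delivery at the other | Yes | Depends on the meaning of *administered* | Depends on the meaning of *administered* |

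Row 1 follows from the set definitions alone, whatever *administered* means. Its scope is small. A Q2W subject has 2 planned injections (1 at each of 2 visits) and a Q4W subject has 4 (2 at each of 2 visits). Either all of these must deliver nothing, or all Visit 1 attempts must fail with no further attempt. Row 2 follows from SAP 8.1.1 and 8.1.2.

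**Step 2: what *administered* means.** SAP 8.1.2 and 8.2.1 present subjects with completed dose delivery as a separate count beside the success count. That count would be 100% by construction if only completed deliveries were in the denominator. Protocol 4.1.1 speaks of an administration being incomplete and asks the healthcare provider to "note the reason why the complete dose was not administered". Both point towards *attempted*. The term is still undefined for an attempt that delivers nothing.

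**Step 3: size.** The plan gives no expected success rate, dropout rate or interval width, so there is no planned figure to reproduce.

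Inputs from the documents: at least 60 users at Visit 1, at least 10 hand-impaired, and exact binomial 90% CIs (SAP 2.4 and 8.1.2). Assumptions: k subjects of the kind in rows 1 or 2 occupy places among the N users, and every other subject succeeds.

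For x successes of n, the Clopper-Pearson limits are the 0.05 quantile of Beta(x, n − x + 1) and the 0.95 quantile of Beta(x + 1, n − x). When x = n, the lower limit is 0.05^(1/n) and the upper limit is 100%. For example, 0.05^(1/58) = 95.0% and 0.05^(1/8) = 68.8%.

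| N | k | As written: (N − k)/(N − k) | Counted as failures: (N − k)/N |
|---|---|---|---|
| 60 | 0 | 60/60 = 100% (95.1 to 100) | the same |
| 60 | 1 | 59/59 = 100% (95.0 to 100) | 59/60 = 98.3% (92.3 to 99.9) |
| 60 | 2 | 58/58 = 100% (95.0 to 100) | 58/60 = 96.7% (89.9 to 99.4) |
| 10 | 1 | 9/9 = 100% (71.7 to 100) | 9/10 = 90.0% (60.6 to 99.5) |
| 10 | 2 | 8/8 = 100% (68.8 to 100) | 8/10 = 80.0% (49.3 to 96.3) |

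**Step 4: if others also fail.** Suppose 2 other subjects fail and are counted either way. With N = 60 and k = 2, the result is 56/58 = 96.6% (89.5 to 99.4) as written, against 56/60 = 93.3% (85.4 to 97.7). The gap of 3.3 points equals that with no other failures (100 − 96.7 = 3.3).

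**The case against.** The best reply is that these cases are rare and mostly visible elsewhere. Subjects have self-injected with the syringe for at least 3 months, must be judged able to use the device, and are trained and observed. Any dose delivered at either visit puts a subject in the SS. The endpoint is defined at Visit 2, so restricting it to those who inject then is a legitimate choice. A Visit 1 failure in a dosed subject still counts in the secondary outcome. Discontinuations are summarised by reason, and disposition is listed for all screened subjects (SAP 5.1). Withdrawal criterion 8 does not require a device cause, so a withdrawal under it need not be a device failure.

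Most of this stands, and it limits the point. It does not remove it: the primary proportion and its interval would still omit these subjects, and SAP 8.1.2 adds a restriction that Protocol 12.3.1 does not state.

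Three stronger readings are tempting but unsupported:

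- *Every failed or partial delivery leaves the denominator.* The separate completed-delivery count argues against this. Partial delivery, and one of two Q4W injections delivered, already score as failures.
- *The protocol counts a missed Visit 2 as failure and the SAP reverses that.* The protocol is silent on how such a subject is scored and also rules out imputation. The mismatch concerns the stated population only.
- *The trial could be declared successful wrongly.* It is an estimation study with no hypothesis test, power target or success threshold.

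**Conclusion.** The point holds in two limited parts. First, the set definitions exclude from both proportions a trained subject whose every attempt delivers no drug. This is certain on the text but narrow. Second, the Visit 2 denominator removes device-related non-attempts from the primary, without support in Protocol 12.3.1 and without an entry in SAP 3.9. The meaning of *administered* needs only clarification.

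Under the assumed counts, one such subject among 60 lowers the estimate by 1.7 points (100 − 98.3), and two lower it by 3.3 points and the lower limit by 5.1 points (95.0 − 89.9). Two of 10 hand-impaired subjects lower that estimate by 20 points, mainly because the subgroup is small. These figures assume that the affected subjects are among the 60 or 10 users and that all others succeed. With none affected, the results are unchanged. The change should be made because it is cheap and the rule is best fixed before results are known.

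**What to change.** 1. Keep the Safety Set unchanged for safety, since the exposure and treatment-emergence windows are anchored on injections.
2. In Protocol 12.1 and SAP 3.5.2, define the FAS as all subjects who started at least one e-Device self-injection attempt after training, whatever amount was delivered. State the operational event that starts an attempt. In SAP 3.5.2 and 8, use the FAS for outcome variables.
3. In SAP 8.1.2 and 8.2.1, replace *administered* with *attempted*, and state that an attempt with no delivery is a failure.
4. Add one supplementary Visit 2 proportion on the FAS that counts non-attempts due to a device problem, an ADE or inability to use the device as failures. Show other non-attempts by reason.
5. Record the departure from Protocol 12.3.1 in SAP 3.9.

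**Cost.** A protocol amendment for the FAS wording, a few SAP sentences, one added proportion and a by-reason display that can build on the planned disposition table. A CRF item for whether an attempt was made may be needed (an assumption, as the CRF is not shown). No new procedure is required: injections are already observed on site, and incomplete ones are documented with the reason. The reported success rate may be slightly lower, and the FAS and SS may differ by a few subjects.
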